5.1.3. Subgroup Analyses for PFS

The primary endpoint will be evaluated for the following subgroups.

- By histological tumor type (uterine and non-uterine) for the mITT population
- Baseline ECOG PS score (0 and 1) for the mITT population
- Prior lines of therapy 1, 2, and 3 (EDC data) for the mITT population
- Prior lines of therapy (4 or more) for the non-mITT population
- Histologic tumor type in combination with number of prior lines of therapy (uterine with 1, 2 and 3 prior lines, non-uterine with 1, 2 and 3 prior lines (EDC data) for the mITT population

5.2. Key Secondary Analyses

5.2.1. Overall Survival

Overall survival (OS) is defined as the time in months from the randomization date to the date of death from any cause or date last known alive for those who did not die.

Specifically,

OS = Date of death or date last known alive - Date of first dose + 1

Subjects will be censored at the last date they are known to be alive. The last known alive date will be the last date of any subject record in the study database. The date may be the last visit date or last contact date that the subject is known to be alive. Subjects who only have baseline record will be censored at the first dose date.

OS will be analyzed using KM methods. A summary table of the number of deaths, the number of censors, and KM estimates (25th, 50th, 75th percentile of OS along with the 95% CI, and OS probability at 3, 6, 9, 12 months, respectively) will be provided by treatment group using the mITT population.

KM curve of OS will be provided using the mITT population.

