8.4.3. Analysis of Key Secondary Efficacy Endpoint

The key secondary endpoint is OS. OS is defined as the time from the randomization date to the date of death from any cause. For subjects who are alive, survival time will be censored at the date of last contact ("last known alive date").

OS will be compared between the two treatment groups, provided the primary endpoint PFS is statistically significant favoring the test treatment arm. A hierarchical testing procedure will be utilized.

Two analyses are planned for OS: the first (interim) at the time of the final analysis for PFS (provided PFS is significant), at which point the information fraction for OS will be at least 60% and a second (final) analysis when 184 events have accumulated. Details will be provided in the study SAP.

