2.2. Modified Intent-to-treat (mITT) Set

The mITT set will include randomized subjects with 1 to 3 prior lines of therapy. The mITT population will be used in all the efficacy analysis, including analyses of the primary and secondary endpoints. Subjects will be grouped based on the group they are randomized to. If a subject receives treatment in the group different from the one to which he/she was randomized, the subject's efficacy data will be analyzed "as randomized." The mITT Analysis Set is the primary analysis population for this study.

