3.2.2. Estimand for Overall Survival (OS)

Research Question: How does survival time compare between unesbulin treatment versus placebo in the population of subjects with unresectable or metastatic, relapsed or refractory LMS?

Subject Population: Subjects previously treated with 1 to 3 prior lines of systemic therapy, who are randomized to a treatment assignment (unesbulin+DTIC or placebo+DTIC) and further described the protocol inclusion exclusion criteria.

Endpoint variable: Time from randomization to death.

Population-level summary: The HR and 95% CI between unesbulin and placebo.

Treatment Condition: unesbulin+DTIC vs. placebo+DTIC

Intercurrent Event Strategy:

- a) Discontinuation of unesbulin Treatment Policy
- b) Discontinuation of DTIC Treatment Policy
- c) Start of subsequent anticancer treatment: Treatment Policy

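### SAP 5.2.1 defines OS from randomization but computes it from first dose, and two 14-week rows of SAP Table 3 mix the same two clocks: small effect, text correction needed

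*SAP*

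**What the plan says.** Three statements start the OS clock at randomization. Protocol 8.4.3: "OS is defined as the time from the randomization date to the date of death from any cause". The OS estimand in SAP 3.2.2: "Time from randomization to death". The opening sentence of SAP 5.2.1: "Overall survival (OS) is defined as the time in months from the randomization date to the date of death from any cause".

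SAP 5.2.1 then gives its only formula: "OS = Date of death or date last known alive - Date of first dose + 1". For living subjects the protocol says "For subjects who are alive, survival time will be censored at the date of last contact", and SAP 5.2.1 says "The last known alive date will be the last date of any subject record in the study database". It adds a special rule: "Subjects who only have baseline record will be censored at the first dose date".

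OS is analysed in the mITT set, which has no dosing condition: "The mITT set will include randomized subjects with 1 to 3 prior lines of therapy". The safety set in SAP 2.3 does require a dose. SAP 3.7 declares no change to the protocol's efficacy analyses.

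SAP Table 3 handles PFS deaths without any post-baseline assessment in two rows. The first counts the death as an event up to 14 weeks after randomization. The second censors it at randomization if it came more than 14 weeks after first dose.

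**The concern.** The formula is the line a programmer would code, and it contradicts the definition above it. Since SAP 3.7 reports no change from the protocol, the first-dose clock is not a declared change of method.

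Three things follow from a literal reading:

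- A randomized, never-dosed mITT subject has no OS time, so an analysis of all randomized subjects with 1 to 3 prior lines silently loses that subject. If such a subject has only a baseline record, the special rule supplies no censoring date either.
- A dosed subject loses the randomization-to-dose interval from OS but not from PFS, which SAP 5.1.1 starts at randomization. The same death can then give an OS time shorter than the PFS time.
- The two Table 3 rows do not meet at a common cut point, so some deaths have no assigned status for the primary endpoint.

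At stake are the OS times of undosed subjects, the Kaplan-Meier percentiles and rates for OS, and the status or date of a few PFS deaths.

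**Working it through.** **1. The clocks side by side**

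| Place | Start of the clock |
|---|---|
| Protocol 8.4.3, OS | randomization |
| SAP 3.2.2, OS estimand | randomization |
| SAP 5.2.1, definition | randomization |
| SAP 5.2.1, formula | first dose |
| SAP 5.1.1, PFS | randomization |
| SAP Table 3, no-scan death, event row | randomization |
| SAP Table 3, no-scan death, censoring row | first dose |

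**2. The plan's own OS figure.** Protocol 8.2 gives 184 events, hazard ratio 0.625 (medians 10 and 16 months), one-sided 0.025 and about 84% power; allocation is 2:1. Schoenfeld's formula: Φ(√(184 × 2/9) × |ln 0.625| − 1.96) = Φ(1.045) = 85.2%. With one O'Brien-Fleming-type look at 60% information it is 84.9%. The plan's figure is reproduced to within about a point, and keeping randomization as the clock leaves it as planned.

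**3. Dosed subjects.** SAP 3.6.1 makes the randomization visit Day 1. Protocol 3.1 gives dacarbazine on Day 1 and unesbulin or placebo on Day 2, so the nominal gap is 0 or 1 day depending on which drug is meant by first dose; section 5.2.1 does not say. The documents set no maximum gap. I assume 0 to 4 calendar days: the ±2 business-day window of Cycle 1 Day 1, stretched over a weekend.

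- Shift per OS time: 4 / 30.4375 = 0.13 months (30.4375 days per month is my assumption).
- Planning medians with a common 4-day gap: 10 − 0.13 = 9.87 and 16 − 0.13 = 15.87 months.
- Hazard ratio: a common shift keeps the order of the times, so the Cox estimate cannot change. One simulated data set of 300 subjects gave 0.663 before and after.
- Wider, variable gaps: over 1,500 simulated trials per setting, with gaps averaging 0, 3, 7 or 14 days in both arms, the mean hazard ratio agreed on the two clocks to within 0.001. In those runs subjects whose follow-up ended before the dosing date dropped out, and usable deaths fell from 184 to 182.5, 180.4 and 176.9 at mean gaps of 3, 7 and 14 days. That loss offsets the shortening: at 14 days the control median went from 9.95 to 10.07 months.
- OS against PFS: for a death 40 days after randomization and a 4-day gap, OS = 36 + 1 = 37 days, while PFS is 40 days, or 41 if it also adds one (SAP 5.1.1 gives no formula).

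**4. Undosed subjects.** Their number is not given. Assume 0% to 3% of the planned 100 placebo and 200 unesbulin subjects: 0 to 3 and 0 to 6. As an extreme case, let all of them die before 3 months and be left out. Survival is taken as exponential with the protocol medians.

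| | Placebo | Unesbulin | Difference |
|---|---|---|---|
| 3-month OS, all subjects | 0.5^(3/10) = 81.23% | 0.5^(3/16) = 87.81% | 6.59 points |
| Undosed left out | 81.23 × 100/97 = 83.74% | 87.81 × 200/194 = 90.53% | 6.79 points |
| Change | +2.51 | +2.72 | +0.20 |

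If the undosed deaths all fell in one arm, the difference would move by −2.51 points (placebo) or +2.72 points (unesbulin).

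**5. Table 3.** 14 weeks = 98 days. The event row ends on day 98 after randomization; the censoring row begins after day 98 + gap.

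- With a gap of 4 days, no-scan deaths on days 99 to 102 fit neither row. With a gap of 0, no dosed subject is affected.
- An undosed subject who dies without a scan after day 98 fits neither row, whatever the gap.
- The last death row, for deaths after more than two missed scans, does not help. It censors at the last adequate assessment, which must be a CR, PR, SD or non-CR/non-PD reading, and these subjects have none.
- Expected deaths in the uncovered band, for 300 subjects at the planning medians: 0.4 for a 1-day gap, 3.0 for 7 days, 5.9 for 14 days. If 5% to 10% of these had no scan (assumed), 0.02 to 0.6 subjects are affected.

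**The case against.** The strongest reply is that nobody could mistake the intent. The protocol, the estimand and the definition sentence all say randomization, and SAP 3.7 says nothing changed, so the formula is a drafting slip. That is fair as to intent, but the formula is the only computational instruction in the section and it is wrong as written.

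The baseline-only rule is a weaker case. It sets a censoring date, not a start date, and for a dosed subject the first-dose date is a valid date known alive. Undosed subjects with any later contact fall under the general last-known-alive rule. What remains is the undosed subject with no post-baseline record, and there may be none.

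The sizes also rest on assumptions. The visit window is not a documented limit on the time from randomization to dosing, and holidays could widen it. The 3-month OS shifts come from an extreme scenario and are not a forecast. For Table 3, the intended handling can be inferred, because other rows censor at randomization when there is no post-baseline assessment. All of this limits the size of the problem; none of it removes the contradictions.

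**Conclusion.** The concern holds, as a minor point. The OS formula contradicts the definition in the same section, and the two Table 3 rows for no-scan deaths use different start dates. Undosed mITT subjects have no OS time under the formula, and a narrow group of PFS deaths has no assigned status.

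In size, an assumed gap of 0 to 4 days costs 0 to 0.13 months per OS time, with no change in the hazard ratio if the gap is common to all. In the extreme illustration with 3% undosed, 3-month OS rises by 2.5 to 2.7 points per arm, but the difference between arms moves by only 0.2 points when the undosed share is equal. Both the gap and the number undosed may be zero.

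The consequence is for estimation and reporting. OS is tested only if PFS is significant (Protocol 8.4.3, SAP 3.3), the data monitoring committee recommended stopping for futility (SAP 3.5), and SAP 5.2.1 itself plans only Kaplan-Meier summaries.

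**What to change.** Change three lines of the SAP:

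1. In 5.2.1, compute OS as the date of death or last known alive date, minus the randomization date, plus 1, and convert it to months with a stated factor; the present formula yields days.
2. In 5.2.1, censor subjects with only a baseline record at the first-dose date if dosed and at the randomization date if never dosed.
3. In Table 3, count the 14 weeks in the censoring row for no-scan deaths from randomization, so that it meets the event row.

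This restores the definition that the protocol and the estimand already give. It needs no new data and no change to the sample size.

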One treatment cycle will constitute 21 days. DTIC will be administered on Day 1 of each 3-week treatment cycle. Unesbulin or placebo tablets will be administered on Days 2 and 5 of Week 1 and Days 1 and 4 of Weeks 2 and 3 of each 3-week treatment cycle (Note: the preferable duration between 2 doses of unesbulin/placebo is approximately 72 hours). Based on the results from a food effect assessment in the ongoing Phase 1b Study PTC596-ONC-007-LMS, it is recommended that unesbulin/placebo be administered with food.

All subjects will receive treatment until evidence of disease progression, unacceptable toxicity, or other withdrawal criteria are met. No crossover will be permitted.

Subjects will undergo weekly assessments throughout the study. The schedule of all study efficacy, safety, PK, and laboratory assessments is shown in Table 1, including a window for completion of the activities associated with each visit. Of note, activities designed to be completed in a single day, for example, PK sampling from before dosing to 8 hours postdose, may not be split up between the 2 days of a window.

An end-of-treatment (EOT) assessment should be performed within 30 days after the end of treatment or until recovery from or stabilization of the AE, whichever occurs latest. For subjects requiring immediate initiation of a new treatment option, the EOT visit may be completed earlier. The EOT assessments are outlined in Table 1. A safety follow-up assessment should be performed by telephone call approximately 30 days (\pm 3 days) after the EOT to assess AEs and concomitant medications. Survival follow-up (sFUP) assessments should be performed by phone every 3 months (\pm 7 days) after the EOT until the later of 184 events or 2 years after the last subject is randomized.

PK Assessment

Approximately 12 randomized subjects will participate in a PK substudy at selected sites. These subjects will be assessed for PK of unesbulin, DTIC, and AIC. The target is for approximately 7 PK evaluable subjects in the unesbulin group to complete Cycle 3.

For the DTIC/AIC PK assessment, blood samples will be collected following an intensive schedule at predose and up to 24 hours postdose on Day 1 of Cycles 1 and 3. Sparse blood samples will be collected at predose and 1.25 and 4 hours postdose (start of infusion) on Day 1 of Cycles 2 and 4.

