6.1.3. Lost to Follow-up

A subject who repeatedly fails to return for scheduled visits and is unable to be contacted by the study site will be considered lost to follow-up.

The following actions should be taken if a subject fails to return to the clinic for a required study visit:

- Attempt to contact the subject and reschedule the missed visit as soon as possible and counsel the subject on the importance of maintaining the assigned visit schedule and determine whether or not the subject wishes to and/or should continue in the study.
- Before a subject is deemed lost to follow-up, the investigator or designee must make every effort to contact the subject. These contact attempts should be documented in the subject's medical record.

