8.2. Sample Size Determination

The sample size for the primary analysis was computed based on the comparison of PFS between subjects randomized to unesbulin plus DTIC and subjects randomized to placebo plus DTIC. The median PFS was assumed to be approximately 1.5 to 2.5 months for the placebo plus DTIC group and more than 4 months for the unesbulin plus DTIC group. With an overall one-sided alpha level of 0.025, a total of 245 events are required to achieve at least 90% power at a hazard ratio of 0.5. Assuming 19 months of enrollment time, a minimum follow-up period of 6 months for the primary endpoint, and approximately 11.5% uniform dropout rate, a total of 300 subjects are planned to be randomized.

One interim analysis will be performed when approximately 36% of the PFS events occur (approximately 88 events). The study may stop for both efficacy and futility. The study may stop for efficacy if the observed hazard ratio is less than 0.447, and the study may stop for futility if the observed hazard ratio is more than 0.67.

The alpha allocation will be controlled separately at the interim and the final analysis timepoints by using the Lan-DeMets spending function that approximates the O'Brien-Fleming approach. The family-wise significance level is 0.025, with 0.000184 allocated at the interim analysis and 0.024816 at the final analysis.

For the key secondary endpoint OS, sample size is based on detecting a hazard ratio of 0.625 (median OS of 10 months versus 16 months, for placebo plus DTIC vs unesbulin plus DTIC, respectively) and a minimum 15-month follow-up. With 184 events (among 265 subjects) a 1-sided 0.025 level log-rank test will have approximately 84% power.

A separate group sequential design and monitoring will be performed for OS, with one interim analysis performed when at least 60% of the OS events occur and a final OS analysis when 184 events occur. The alpha allocation will be controlled by using the Lan-DeMets spending function that approximates the O'Brien-Fleming approach.

Data from the additional 45 subjects enrolled with at least 4 prior lines of therapy will not be included in the primary analysis; rather, the efficacy analysis of data from these subjects will be considered exploratory and included as a sensitivity analysis only.

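### The SAP's last known alive date takes any database record, which is broader than evidence of life, so the Kaplan-Meier OS estimates could be inflated if such records exist

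*SAP*

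**What the plan says.** SAP 5.2.1 gives three consecutive statements on censoring for OS.

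- The principle: "Subjects will be censored at the last date they are known to be alive".
- The derivation: "The last known alive date will be the last date of any subject record in the study database".
- A gloss: "The date may be the last visit date or last contact date that the subject is known to be alive".

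Protocol 8.4.3 has one rule: "For subjects who are alive, survival time will be censored at the date of last contact", and it equates that date with the last known alive date.

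On how survival is followed, protocol 3.1 says that survival follow-up "assessments should be performed by phone every 3 months". Protocol 6.1.3 says that a subject who repeatedly misses visits and "is unable to be contacted by the study site will be considered lost to follow-up". The same section asks that attempts to reach such a subject be documented in the medical record.

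SAP 3.7 declares no change to the protocol's efficacy analyses. SAP 4.8 says how the data cut-off applies to the last dose date; SAP 5.2.1 has no such provision for the last known alive date.

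**The concern.** The derivation sentence is the one a programmer would code, and it is wider than the principle it serves. Not every dated record shows that a subject was alive on that date. Possible exceptions are an entry for a survival call that reached nobody, the date of a central read or an assay, a data-entry date, or a record dated after the cut-off.

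If such a record supplies the censoring date, a lost subject stays in the risk set after real contact ended. A death in that interval is not seen, but the time is still counted as survival. Kaplan-Meier quantiles and survival probabilities then come out too high. OS is the key secondary endpoint, and SAP 5.2.1 still plans quartiles, survival probabilities at 3, 6, 9 and 12 months, and a curve.

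**Working it through.** **Step 1: the text.** The principle and protocol 8.4.3 both require evidence of life. The derivation requires only a record. The gloss says what the date may be, so it illustrates the derivation without restricting it. No list of qualifying records is given, no record type is excluded, and no cut-off cap is set. The stated rule is therefore wider than its own principle.

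**Step 2: the plan's own OS figure.** Inputs from protocol 8.2: "sample size is based on detecting a hazard ratio of 0.625 (median OS of 10 months versus 16 months"), 184 events and one-sided 0.025. Allocation is 2:1 (protocol 5.6). By Schoenfeld's formula:

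- z = √(184 × 2/3 × 1/3) × |ln 0.625| − 1.960 = 6.394 × 0.470 − 1.960 = 1.045
- power = Φ(1.045) = 0.852, or 0.849 with an O'Brien-Fleming-type interim at 60% information

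This agrees with the stated power of approximately 84%. The figure does not depend on the censoring rule, so the fix does not alter it.

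**Step 3: size if the rule were applied literally.** Survival was simulated as exponential with medians of 16 and 10 months, 2:1, 19 months of accrual and 15 months of further follow-up (19 + 15 = month 34). Each lost subject's censoring date was moved later by an assumed lag, with deaths in the gap left unobserved. There were 1,500 runs per setting; Monte Carlo error on the hazard ratio (HR) is about 0.005.

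The loss rate is an assumption. Protocol 8.2 gives approximately 11.5% dropout for the PFS sizing, with no time unit, and nothing for OS. Two readings were used, each with equal loss and equal lag in both arms:

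| Reading of 11.5% | Lag | Unesbulin median (months) | Rise | HR |
|---|---|---|---|---|
| Spread over roughly two years (N = 265, about 17 to 18 lost) | 0 | 16.1 | – | 0.62 |
| | 3 months | 16.3 | 0.2 | 0.63 |
| | 6 months | 16.5 | 0.4 | 0.63 |
| Per year (N = 300) | 0 | 16.1 | – | 0.62 |
| | 3 months | 16.5 | 0.4 | at most 0.64 |
| | 6 months | 16.9 | 0.8 | at most 0.64 |

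On the first reading the placebo median goes from 10.1 to 10.3 and 10.4 months. With no true effect, one-sided type I error is 0.026 with no lag and 0.026 to 0.028 with equal lag (4,000 runs).

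**Step 4: what it takes to move the HR.** The arms must differ. These cases are illustrations only.

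- *Unequal lag*, first reading: 6 months of lag in the unesbulin arm only gives HR 0.60 and, under the null, type I error 0.040. In the placebo arm only, it gives HR 0.64 and type I error 0.018.
- *Unequal loss, same lag*: with assumed yearly loss of 15% on unesbulin and 5% on placebo, a 3 to 6 month lag takes the HR from about 0.625 to about 0.60 or 0.61. With the loss reversed, it goes from 0.62 to between 0.64 and 0.66.

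No document gives loss or lag by arm.

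**The case against.** The strongest reply is that the three SAP sentences should be read together. The sentences on either side of the derivation speak of the subject being known to be alive, and the protocol treats last contact and last known alive as the same date. On that reading, a record that does not show life cannot supply the date. This stands as evidence of intent, but it does not remove the conflict: the derivation sentence is definite, and the sentence after it is only permissive.

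The second reply is that no document shows that such records exist in the database. Protocol 6.1.3, which concerns missed clinic visits, sends contact attempts to the medical record, and no section says that failed survival calls are entered in the database. Reader, assay and data-entry dates are plausible but unproven. Output specifications are in a separate document that is not available here. This stands in full and makes the bias conditional.

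The third reply is that little turns on it. SAP 3.5 records that the Data Monitoring Committee recommended stopping for futility. OS is tested only if PFS is significant (protocol 8.4.3, SAP 3.3), and SAP 5.2.1 itself lists only Kaplan-Meier summaries. The simulations also assume the full planned trial. This stands too, and it limits the consequence to descriptive estimates.

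A reader might go further and infer that the rule biases the OS hazard ratio, or favours the arm with more loss to follow-up. The documents do not support that. It needs a difference between arms in loss or in lag, and none is stated or implied.

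**Conclusion.** The point holds as an over-broad derivation rule with a conditional effect. SAP 5.2.1 departs from the protocol's last-contact rule and from its own principle, and SAP 3.7 does not declare the departure.

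Whether OS is actually biased depends on two things the documents leave open: that the rule is applied literally, and that the database holds dated records which do not show life. If both are true, the Kaplan-Meier estimates are too high. Under the assumed losses and lags above, the unesbulin median rises by about 0.2 to 0.8 months, while the HR stays near 0.62 to 0.64 when the arms are alike. If no such records exist, the effect is near zero. Subjects with a recorded death are unaffected, because they are dated at death.

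The change is worth making because the planned descriptive OS results rest on this date. The documents do not show that a confirmatory conclusion is at risk.

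**What to change.** Replace the derivation sentence in SAP 5.2.1 with:

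*The last known alive date is the latest date, on or before the data cut-off, of a record showing the subject alive (visit, dosing, scan or sample collection, AE onset, or survival contact with status alive); unsuccessful contact attempts and reader, assay, data-entry or imputed dates are not used.*

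This restores agreement with protocol 8.4.3 and with the SAP's own principle. It costs one sentence and one derivation, and needs no new data. The downside is slightly shorter follow-up for a few censored subjects.
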